### **8.3 Emergency unblinding of treatment assignment**

Not applicable.

### **8.4 Pregnancies**

To ensure patient safety, each pregnancy occurring while the patient is on study treatment must be reported to Novartis within 24 hours of learning of its occurrence. The pregnancy should be followed up to determine outcome, including spontaneous or voluntary termination, details of the birth, and the presence or absence of any birth defects, congenital abnormalities, or maternal and/or newborn complications.

Pregnancy should be recorded on a Clinical Trial Pregnancy Form and reported by the investigator to the oncology Novartis Drug Safety and Epidemiology Department (DS&E). Pregnancy follow-up should be recorded on the same form and should include an assessment of the possible relationship to the study treatment of any pregnancy outcome. Any SAE experienced during pregnancy must be reported on the SAE Report Form.

Pregnancy outcomes must be collected for the female partners of any males who took study treatment in this study. Consent to report information regarding these pregnancy outcomes should be obtained from the mother.

Preclinical data regarding reproductive toxicity is described in the most recent Investigator Brochure. The potential reproductive risk for humans is unknown. Women of childbearing potential should be advised to use highly effective contraception methods while they are receiving everolimus and up to 8 weeks after treatment has been stopped. If a pregnancy occurs while on study treatment, the newborn will be followed for at least 12 months.

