### 5.3 Exclusion criteria

Patients eligible for this study must not meet **any** of the following criteria:

1. Patient has been permanently discontinued from everolimus study treatment in the parent study.
2. Patients who are receiving everolimus in combination with unapproved or experimental treatments.
3. Sexually active males, unless they use a condom during intercourse while taking drug and for 8 weeks after stopping study medication. Males also should not father a child in this period. A condom is required to be used also by vasectomized men in order to prevent delivery of the drug via seminal fluid.
4. Pregnant or nursing (lactating) women, where pregnancy is defined as the state of a female after conception and until the termination of gestation, confirmed by a positive hCG laboratory test.
5. Women of child-bearing potential, defined as all women physiologically capable of becoming pregnant, **unless** they are using highly effective methods of contraception during dosing and for 8 weeks after stopping study treatment.
  - Women are considered post-menopausal and not of child-bearing potential if they have had 12 months of natural (spontaneous) amenorrhea with an appropriate clinical profile (e.g. age appropriate, history of vasomotor symptoms) or have had surgical bilateral oophorectomy (with or without hysterectomy) or tubal ligation at least six weeks prior to randomization. In the case of oophorectomy alone, only when the reproductive status of the woman has been confirmed by follow up hormone level assessment is she considered not of child-bearing potential

**Highly effective** contraception methods include:

- Total abstinence: When this is in line with the preferred and usual lifestyle of the subject. [Periodic abstinence (e.g., calendar, ovulation, symptothermal, post-ovulation methods) and withdrawal are not acceptable methods of contraception].
- Female Sterilization: Have had surgical bilateral oophorectomy (with or without hysterectomy) or tubal ligation at least six weeks before taking study treatment. In case of oophorectomy alone, only when the reproductive status of the woman has been confirmed by follow up hormone level assessment.
- Male partner sterilization (at least 6 months prior to enrolling). [For female study subjects, the vasectomized male partner should be the sole partner for that patient]

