- Use of oral, injected or implanted hormonal methods of contraception or placement of an intrauterine device (IUD) or intrauterine system (IUS), or other forms of hormonal contraception that have comparable efficacy (failure rate <1%), for example hormone vaginal ring or transdermal hormone contraception.
- In case of use of oral contraception, women should have been stable on the same pill before taking study treatment.

If a study patient becomes pregnant or suspects being pregnant during the study or within 30 days after the final dose of everolimus, the investigator needs to be informed immediately and ongoing study treatment with everolimus has to be stopped immediately.

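### For female patients, pregnancy reporting in Protocol 8.4, notification in 5.3 and the 8-week contraception period do not line up, and no rule covers a pregnancy arising in days 31 to 56 after the last dose

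*Protocol*

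**What the plan says.** Three provisions bear on a pregnancy in a female patient.

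- **Contraception.** Section 5.3 admits women of child-bearing potential only if they are "using highly effective methods of contraception during dosing and for 8 weeks after stopping study treatment". Section 8.4 repeats the period: "while they are receiving everolimus and up to 8 weeks after treatment has been stopped".
- **Notice to the investigator.** Under 5.3 the investigator must be informed at once if a patient "becomes pregnant or suspects being pregnant during the study or within 30 days after the final dose of everolimus".
- **Report to the sponsor.** Section 8.4 states that "each pregnancy occurring while the patient is on study treatment must be reported" to the sponsor, within 24 hours of the site becoming aware. Follow-up of the newborn for at least 12 months is also conditional on the pregnancy occurring on study treatment.

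For male patients, 5.3 sets the same 8 weeks for condom use. Section 8.4 asks for pregnancy outcomes in the partners of any man who took study treatment and gives no time limit.

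The last scheduled pregnancy test is at the End of Treatment visit (7.2.2, Table 7-1). The last contact is 30 days after the last dose, may be by telephone, and asks about adverse events (7.1.6). After that, an SAE is reported only if the investigator suspects a causal link to study treatment (8.2.2).

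**The concern.** The protocol treats the 8 weeks after the last dose as a period in which pregnancy should be avoided, and 8.4 describes the reproductive risk in humans as unknown. A protocol that asks women to avoid pregnancy over a stated period would be expected to capture pregnancies that occur in it. Here the reporting duty stops at the end of treatment if 8.4 is taken literally, and the notification duty stops at day 30.

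Two things are at stake. A pregnancy inside the precaution period might not reach the sponsor, and the infant might not be followed. In addition, long-term safety is the primary objective, and developmental and reproductive toxicity are among the risks that 8.1.3 asks sites to report on the SAE form. Without a pregnancy record, a site has no required route to learn the outcome on which such a report would depend.

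**Working it through.** The plan gives no figure to reproduce, so the check compares the windows in days after the last dose.

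**Inputs**

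| Provision | Source | Last day covered |
|---|---|---|
| Contraception, women | 5.3 and 8.4 | 8 × 7 = 56 |
| Patient's pregnancy notified to investigator | 5.3 | 30 |
| Pregnancy reported to sponsor | 8.4 | 0 (on treatment only) |
| Newborn follow-up | 8.4 | 0 (on treatment only) |
| Last pregnancy test | 7.2.2, Table 7-1 | End of Treatment visit |
| Last safety contact | 7.1.6 | 30 |
| Partner-pregnancy outcomes | 8.4 | No limit stated |

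**Uncovered part of the 56 days, female patients**

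- Against 8.4 read literally: 56 − 0 = 56 days.
- Against 5.3: 56 − 30 = 26 days (days 31 to 56), and 26/56 = 46%.

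**Does a generous reading of 8.4 close the gap?** Sections 10.5.3.1 of the protocol and 2.8 of the SAP define the on-treatment period for analysis as running to 30 days after the last dose. If 8.4 borrowed that definition, days 1 to 30 would be covered, but the same 26 days would remain.

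**What other provisions catch**

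- A pregnancy that began on treatment and was learned of later is still reportable under 8.4. However, no test follows End of Treatment, and the 30-day contact does not mention pregnancy.
- A congenital anomaly is an SAE (8.2.1) and remains reportable after day 30 if suspected to be related (8.2.2). The pregnancy itself, an uncomplicated outcome, and an anomaly not suspected to be related are not reportable by that route.

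**Is drug exposure shown in days 31 to 56?** Section 1.2.1.2 (Pharmacokinetics) gives a mean terminal half-life of 30 hours. Thirty days is 30 × 24 = 720 hours, and 720/30 = 24 half-lives. The remaining fraction is 0.5^24, about 6 × 10⁻⁸. On that figure the documents do not show exposure in the later weeks.

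**The case against.** The strongest reply is that the windows govern different acts: prevention, notice from patient to site, and report from site to sponsor. A site can comply with all three at once, and a precaution period longer than a reporting period can be a deliberate choice. That stands against calling them a three-way contradiction. It does not explain what a site should do with a pregnancy notified under 5.3 on, say, day 15, because 8.4 read literally creates no duty to pass it on.

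It can also be argued that days 1 to 30 are covered in substance. The second paragraph of 8.4 says pregnancy should be recorded on the pregnancy form and reported, without repeating the on-treatment condition, and 5.3 brings such cases to the investigator. This is a fair reading, but not the only one. It also leaves days 31 to 56 with no duty on the patient to notify.

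A reader might infer three stronger points, none of which the documents support.

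- **A gap for partners of male patients.** The partner sentence in 8.4 has no time limit, so it is not shorter than 8 weeks.
- **Unreported exposed pregnancies.** The half-life calculation does not show exposure in days 31 to 56. The 8 weeks is the protocol's precaution period and should be described as that.
- **Undercounted AESI tables.** The AESIs are toxicities, not pregnancy itself, and related anomalies remain reportable. The planned AE and AESI summaries use the period ending 30 days after the last dose (SAP 2.8, 2.8.2, 2.8.2.1). Later events are only listed and flagged, so those tables would not change.

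**Conclusion.** The concern holds for female patients' own pregnancies. Section 8.4 does not clearly send to the sponsor a pregnancy notified in days 1 to 30. No passage requires one arising in days 31 to 56 to be notified, reported or followed. The clear gap is 26 of 56 days, or 46% of the period the protocol itself sets. It becomes the full 56 days only on the literal reading of 8.4.

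The practical size is small. SAP 2.1 puts enrolment at 34 patients. The number of women of child-bearing potential is not given, so no expected count can be calculated, but few or no cases are likely. The point matters because each case is an individual safety matter, not because it would shift a summary. It rests on taking 8 weeks as 56 days, counting from the last dose, and reading the sections as written. It is a correction that should be made, and it does not affect the validity of the planned analyses.

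**What to change.** Reconcile 5.3 and 8.4 so that one window, stated identically in both, governs notification to the investigator, reporting to the sponsor and newborn follow-up for female patients. That window should not be shorter than the contraception period the protocol already sets.

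At the existing 30-day safety contact (7.1.6), ask about pregnancy and remind the patient to tell the site of any pregnancy until the window ends. The question alone cannot detect a pregnancy that arises after day 30, so the reminder is needed.

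The cost is amendment wording and a few more weeks of reporting duty for sites. No visit or test is added. The limitation is that ascertainment after day 30 would rely on patients coming forward.

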### **8.5 Warnings and precautions**

No evidence available at the time of the approval of this study protocol indicated that special warnings or precautions were appropriate, other than those noted in the provided Investigator Brochure. Additional safety information collected between IB updates will be communicated in the form of Investigator Notifications. This information will be included in the patient informed consent and should be discussed with the patient during the study as needed.

### **8.6 Data Monitoring Committee**

Not applicable.

## **8.7 Steering Committee**

Not applicable.

## **9 Data collection and management**

### **9.1 Data confidentiality**

Information about study subjects will be kept confidential and managed under the applicable laws and regulations. Those regulations require a signed subject authorization informing the subject of the following:

- What protected health information (PHI) will be collected from subjects in this study
- Who will have access to that information and why
- Who will use or disclose that information
- The rights of a research subject to revoke their authorization for use of their PHI.

In the event that a subject revokes authorization to collect or use PHI, the investigator, by regulation, retains the ability to use all information collected prior to the revocation of subject authorization. For subjects that have revoked authorization to collect or use PHI, attempts should be made to obtain permission to collect follow-up safety information (e.g. has the subject experienced any new or worsened AEs) at the end of their scheduled study period.

The data collection system for this study uses built-in security features to encrypt all data for transmission in both directions, preventing unauthorized access to confidential participant information. Access to the system will be controlled by a sequence of individually assigned user identification codes and passwords, made available only to authorized personnel who have completed prerequisite training.

### **9.2 Site monitoring**

Before study initiation, at a site initiation visit or at an investigator's meeting, Novartis personnel (or designated CRO) will review the protocol and CRFs with the investigators and their staff. During the study, the field monitor will visit the site regularly to check the completeness of patient records, the accuracy of entries on the CRFs, the adherence to the protocol to Good Clinical Practice, the progress of enrollment, and to ensure that study treatment is being stored, dispensed, and accounted for according to specifications. Key study personnel must be available to assist the field monitor during these visits.

The investigator must maintain source documents for each patient in the study, consisting of case and visit notes (hospital or clinic medical records) containing demographic and medical information, laboratory data, electrocardiograms, and the results of any other tests or assessments. All information recorded on CRFs must be traceable to source documents in the patient's file. The investigator must also keep the original signed informed consent form (a signed copy is given to the patient).

The investigator must give the monitor access to all relevant source documents to confirm their consistency with the CRF entries. Novartis monitoring standards require full verification for the presence of informed consent, adherence to the inclusion/exclusion criteria and

documentation of SAEs. Additional checks of the consistency of the source data with the CRFs are performed according to the study-specific monitoring plan.

### **9.3 Data collection**

For studies using Electronic Data Capture (EDC), the designated investigator staff will enter the data required by the protocol into the Electronic Case Report Forms (eCRF). The eCRFs have been built using fully validated secure web-enabled software that conforms to 21 CFR Part 11 requirements, Investigator site staff will not be given access to the EDC system until they have been trained. Automatic validation programs check for data discrepancies in the eCRFs and, allow modification or verification of the entered data by the investigator staff.

The Principal Investigator is responsible for assuring that the data entered in eCRFs is complete, accurate, and that entry and updates are performed in a timely manner.

### **9.4 Database management and quality control**

For studies using eCRFs, Novartis personnel (or designated CRO) will review the data entered by investigational staff for completeness and accuracy. Electronic data queries stating the nature of the problem and requesting clarification will be created for discrepancies and missing values and sent to the investigational site via the EDC system. Designated investigator site staff are required to respond promptly to queries and to make any necessary changes to the data.

At the conclusion of the study, the occurrence of any protocol violations will be determined. After these actions have been completed and the data has been verified to be complete and accurate, the database will be declared locked and made available for data analysis. Authorization is required prior to making any database changes to locked data, by joint written agreement between the Global Head of Biostatistics and Data Management and the Global Head of Clinical Development.

For EDC studies, after database lock, the investigator will receive a CD-ROM or paper copies of the patient data for archiving at the investigational site.

## **10 Statistical methods and data analysis**

### **10.1 Analysis sets**

The following sets will be used for statistical analysis and data reporting.

#### **10.1.1 Full Analysis Set**

Not applicable.

#### **10.1.2 Safety set**

The Safety Set includes all patients who received at least one dose of study medication after enrolling into the roll-over protocol.

### **10.1.3 Dose-determining analysis set**

Not applicable.

### **10.2 Patient demographics/other baseline characteristics**

Demographic and other baseline data characteristics will be summarized descriptively for the Safety Set.

### **10.3 Treatments (study treatment, compliance)**

Dose administration data will be summarized using the Safety Set.

### **10.4 Primary objective**

The primary objective is to evaluate long term safety as assessed by the occurrence of AEs/SAEs.

#### **10.4.1 Variable**

See Section 10.5.3.

#### **10.4.2 Statistical hypothesis, model, and method of analysis**

No hypothesis will be tested.

#### **10.4.3 Handling of missing values/censoring/discontinuations**

Not applicable.

#### **10.4.4 Supportive and Sensitivity analyses**

No supportive analysis will be performed.

### **10.5 Secondary objectives**

#### **10.5.1 Key secondary objective(s)**

Not applicable.

#### **10.5.2 Other secondary efficacy objectives**

[figure not shown]
The secondary objective of the study is to evaluate clinical benefit as assessed by the investigator. Proportion of patients with clinical benefit as assessed by the investigator will be summarized at scheduled visits.

#### **10.5.3 Safety objectives**

The assessment of safety will be based mainly on the frequency of AEs and SAEs.

##### **10.5.3.1 Analysis set and grouping for the analyses**

The overall observation period will be divided into two mutually exclusive segments:

1. on-treatment period: from day of first dose of study medication in the roll-over study to 30 days after last dose of study medication
2. post-treatment period: starting at day 30+1 after last dose of study medication.

#### **10.5.3.2 Adverse events (AEs)**

Summary tables for adverse events (AEs) will include only AEs that started or worsened during the on-treatment period, the *treatment-emergent* AEs. However, all safety data (including those from the post-treatment periods) will be listed and those collected during the post-treatment period are to be flagged.

The incidence of treatment-emergent adverse events (new or worsening from baseline) will be summarized by system organ class and or preferred term, severity (based on CTCAE grades), type of adverse event, relation to study treatment.

Deaths reportable as SAEs and non-fatal serious adverse events will be listed by patient and tabulated by type of adverse event.

#### **10.5.3.3 Other safety data**

Not applicable.

#### **10.5.3.4 Supportive analyses for secondary**

Not applicable.

#### **10.5.3.5 Tolerability**

Not applicable.

#### **10.5.3.6 Pharmacokinetics**

Not applicable.

### **10.6 Exploratory objectives**

Not applicable.

### **10.7 Interim analysis**

Not applicable.

### **10.8 Sample size calculation**

Not applicable.

### **10.9 Power for analysis of key secondary variables**

Not applicable.

## **11 Ethical considerations and administrative procedures**

### **11.1 Regulatory and ethical compliance**

This clinical study was designed, shall be implemented and reported in accordance with the ICH Harmonized Tripartite Guidelines for Good Clinical Practice, with applicable local regulations (including European Directive 2001/20/EC and US Code of Federal Regulations Title 21), and with the ethical principles laid down in the Declaration of Helsinki.

### **11.2 Responsibilities of the investigator and IRB/IEC/REB**

The protocol and the proposed informed consent form must be reviewed and approved by a properly constituted Institutional Review Board/Independent Ethics Committee/Research Ethics Board (IRB/IEC/REB) before study start. Prior to study start, the investigator is required to sign a protocol signature page confirming his/her agreement to conduct the study in accordance with these documents and all of the instructions and procedures found in this protocol and to give access to all relevant data and records to Novartis monitors, auditors, Novartis Clinical Quality Assurance representatives, designated agents of Novartis, IRBs/IECs/REBs and regulatory authorities as required.

### **11.3 Informed consent procedures**

Eligible patients may only be included in the study after providing written (witnessed, where required by law or regulation), IRB/IEC/REB-approved informed consent

Informed consent must be obtained before conducting any study-specific procedures (i.e. all of the procedures described in the protocol). The process of obtaining informed consent should be documented in the patient source documents. The date when a subject's Informed Consent was actually obtained will be captured in their CRFs.

Novartis will provide to investigators, in a separate document, a proposed informed consent form (ICF) that is considered appropriate for this study and complies with the ICH GCP guideline and regulatory requirements. Any changes to this ICF suggested by the investigator must be agreed to by Novartis before submission to the IRB/IEC/REB, and a copy of the approved version must be provided to the Novartis monitor after IRB/IEC/REB approval.

Women of child bearing potential should be informed that taking the study medication may involve unknown risks to the fetus if pregnancy were to occur during the study and agree that in order to participate in the study they must adhere to the contraception requirement for the duration of the study. If there is any question that the patient will not reliably comply, they should not be entered in the study.

#### **Additional consent form**

Not applicable.

## **11.4 Discontinuation of the study**

Novartis reserves the right to discontinue this study under the conditions specified in the clinical study agreement. Specific conditions for terminating the study are outlined in [Section 4.4](#).

## **11.5 Publication of study protocol and results**

Novartis assures that the key design elements of this protocol will be posted in a publicly accessible database such as [clinicaltrials.gov](http://clinicaltrials.gov). In addition, upon study completion and finalization of the study report the results of this study will be either submitted for publication and/or posted in a publicly accessible database of clinical study results.

[figure not shown]
